#### 4.10.2.6. Microbiology pathogen

Sputum sample or oropharyngeal swab for microbiology organism identification are collected prior to and after treatment. Number and frequency of observed pathogens (included details for others) will be provided by time point.

The following format will be displayed for (CRF defined categories and Others)

**Table 27: Microbiology Pathogen List**

Reported	Formatted	Flag for Pseudomonas
Terms from the coded list		
Achromobacter xylosoxidans		
Aspergillus spp		
Burkholderia spp		
Candida spp		
Hemophilus influenzae		

Inquilinus limosus		
Non-tuberculous mycobacterium - MAC		
Non-tuberculous mycobacterium - M.cheloni or M. abscessus		
Pandoraea apista		
Pseudomonas aeruginosa		Y
Ralstonia spp		
Staphylococcus aureus		
Stenotrophomonas maltophilia		
Terms from the Other category (free text)		
'commensal bacteria	Normal Flora	
BURKHOLDERIA CENOCEPACIA, STAFYLOCOCCUS AEREUS, YEAST	This is three different pathogens: Burkholderia spp, Staphylococcus aureus, Yeast spp  * will be consider "Others", or in separate if the data changes.	
Escherichia coli	Escherichia coli	
MRSA	Staphylococcus aureus	
Methicillin Resistant Staph aureus	Staphylococcus aureus	
Methicillin-Resistant Staphylococcus	Staphylococcus aureus	
Mucoid Pseudomonas Aeruginosa	Pseudomonas aeruginosa	Y
Mycobacterium fortuitum	Mycobacterium fortuitum	
Normal Flora	Normal Flora	
PROTEUS MIRABILIS	Proteus mirabilis	
Pseudomonas positive	Pseudomonas aeruginosa	Y
Yeast	Yeast spp	

enterobacter asburiae	Enterobacter spp	
enterobacter cloacae	Enterobacter spp	
fungi (non specific)	Fungi spp	
haemophilus parainfluenzae	Haemophilus parainfluenzae	
haemophilus influenza-candida albicans/dubliniensis	This is multiple pathogens: Haemophilus influenza, and Candida spp,	
micro organism filamentous fungus evoking	Fungi spp	
microbiota reasident	Normal flora	
microbiota resident	Normal flora	
mold	Mold spp	
proteus mirabilis	Proteus mirabilis	
staphylococcus aureus	Staphylococcus aureus	
yeast	Yeast spp	
yeasts	Yeast spp	

The list may be updated based on latest database.

#### 4.10.2.7. Parameters collected at baseline only

Descriptive summaries of actual values will be reported for the following parameters: Tocopherol Vitamin E (continuous reporting) and Drug screen (categorical Negative/Positive).

#### 4.10.2.8. Pregnancy test

Pregnancy test results will be presented in a by subject data listing.

#### 4.10.3. Vital Signs and Oximetry

Descriptive summaries of actual values and changes from baseline of vital signs will be reported for each time point, in the following parameters: Height (baseline only), Weight, BMI, Heart rate, Systolic and Diastolic Blood Pressure, Temperature, Pulse rate and Pulse Oximetry.

By-subject listings of vital sign measurements will be presented including flag for abnormality (if exist). A special listing reporting vital signs measurements considered clinically relevant will be provided.

4.10.4. Physical Examinations

Physical examination abnormal findings will be presented in a by subject data listing.

4.10.5. Electrocardiogram

12-Lead Standard electrocardiogram data are collected as Normal/Abnormal. Number and percentage of Normal/Abnormal Not Clinically Significant/Abnormal Clinically Significant values will be presented overall (number of subjects) and by visit (prior to treatment and post treatment (Day 8 for SAD, Day 33 for MAD).

Clinically Significant Abnormal ECG results with comments will be reported in listings.

4.10.6. Prior and Concomitant Medications

Concomitant medications are to be coded using the WHO Drug dictionary.

Prior and Concomitant Medications will be tabulated separately by ATC level 2 and Preferred Name (number and percent of subjects). Tables will be sorted by alphabetical order of ATC level 2 and Preferred Name.

## **5. CHANGES TO PLANNED ANALYSES**

As of this date, there have been no changes between the protocol-defined statistical analyses and pharmacokinetics analyses those presented in this statistical plan.

## 7. APPENDICES

### APPENDIX 1: SCHEDULE OF ASSESSMENTS

**Table A.1-1: Single Ascending Dose Cohorts 1-4**

Study Procedures	Screening	Check-In				Discharge				End of Study
Study Day	≤-14 days a	-1	1 b	2	3	4	5	6	7	8
In Hours		-24	0	24	48	72	96	120	144	168
Informed consent	X									
Demographics	X									
Medical History	X									
Eligibility Review	X	X								
Concomitant Medications	X	X	X	X	X	X				X
Adverse Events		X	X	X	X	X				X
Physical Exam	C	C	S	S		S				C
Height & Weight	H/W	W	W							W
Vital Signs c & Oximetry	X	X	X	X	X	X				X
Spirometry d	X	X	X	X		X				X
Chest Xray	X e									X f
12-lead ECG	X									X
24-Hour Telemetry			X							
Blood for Safety Labs g	X	X h	X	X	X	X				X
Urinalysis g	U	U h	U	U	U	U				U
Drug Screen g	X									
Pregnancy Test g,i	X	X								X
Sputum for Microbiology g		X								X
Blood for CFTR g	Genotyping	Sequencing								
Biomarkers g	X	X		X		X				X
Sweat Chloride g	X									
Randomization		X								

Study Procedures	Screening	Check-In				Discharge				End of Study
Study Drug Administration j			X							
Collect Samples for PK g			X	X	X	X				X

Abbreviations: C = complete physical exam; H = height; S = symptom-directed physical exam; U = urinalysis (dipstick); W = weight
 
a The screening period for an individual subject may be extended for an additional 7 days at the discretion of the Sponsor's Medical Monitor. See Protocol Section 7.2 for details.
 
b See Protocol Section Section 7.3.2 for details on timing of these assessments relative to study drug administration on Day 1.
 
c Includes blood pressure, heart rate, respiratory rate, and temperature.
 
d Includes FEV1, FVC, and FEF25-75.
 
e A Chest Xray or CT scan obtained within 90 days of screening is acceptable if there was no intercurrent pulmonary illness during the interim.
 
f Only subjects who experience pulmonary AEs during the study.
 
g See Protocol Appendix 2 for a detailed schedule of these assessments, broken down by type of specimen and time relative to dose.
 
h Only laboratory assessments that are abnormal (but not clinically significant) at screening should be repeated at Day-1.
 
i Pregnancy test (preferably serum but urine is accepted) required for women of childbearing potential only.
 
j Subjects who are taking concurrent CF therapy should receive this therapy prior to study drug dosing in the order specified in Protocol Section 6.3.1.
										

**Table A.1-2: Multiple Ascending Dose Cohorts 5-8, WEEK 1**  
**Dosing Schedule assumes Monday-Wednesday-Friday dosing:**

Study Procedures	Screening		Dose 1	Dose 2		Dose 3		
Study Day	≤-14 days a	-1	1	3	4	5	6	7
In Hours Post Dose 1		-24	0	48	72	96	120	144
Informed consent	X							
Demographics	X							
Medical History	X							
Eligibility Review	X	X						
Concomitant Medications	X	X	X	X	X	X		
Adverse Events		X	X	X	X	X		
Physical Exam	C	C	S	S	S	S		
Height & Weight	H/W	W	W					
Vital Signs b & Oximetry	X	X	X	X	X	X		
Spirometry c	X	X	X	X	X	X		
Chest Xray	X d							
12-lead ECG	X							
Telemetry			X					
CFQ-R RSS e			X					
Blood for Safety Labs f	X	X g	X	X	X			
Urinalysis f	U	U g	U	U	U			
Drug Screen f	X							
Pregnancy Test f,h	X	X						
Sputum for Microbiology f		X						
Blood for CFTR f	Genotyping	Sequencing						
Biomarkers f	X	X			X			
Sweat Chloride f	X							
Randomization		X						
Study Drug Administration i			X	X		X		

Study Procedures	Screening		Dose 1	Dose 2		Dose 3		
Collect Samples for PK f			X	X	X	X		

Abbreviations: C = complete physical exam; CFQ-R RSS = Cystic Fibrosis Questionnaire-Revised Respiratory Symptom Score; ECG = electrocardiogram; H = height; PK = pharmacokinetic; S = symptom-directed physical exam; U = urinalysis (dipstick); W = weight
 
NOTE: See also Protocol Section 7.4 for details on timing of assessments relative to study drug administration.
 
a The screening period for an individual subject may be extended for an additional 7 days at the discretion of the Sponsor's Medical Monitor. See Protocol Section 7.2 for details.
 
b Includes blood pressure, heart rate, respiratory rate, and temperature.
 
c Includes FEV1, FVC, and FEF25-75.
 
d A Chest Xray or CT scan obtained within 90 days of screening is acceptable if there was no intercurrent pulmonary illness during the interim.
 
e Should be completed prior to any other procedures or assessments.
 
f See Protocol Appendix 2 for a detailed schedule of these assessments, broken down by type of specimen and time relative to dose.
 
g Only laboratory assessments that are abnormal (but not clinically significant) at screening should be repeated at Day-1.
 
h Pregnancy test (preferably serum but urine is accepted) required for women of childbearing potential only.
 
i Subjects who are taking concurrent CF therapy should receive this therapy prior to study drug dosing in the order specified in Protocol Section 6.3.1.
								

**Table A.1-3: Multiple Ascending Dose Cohorts 5-8, WEEK 2**

Study Procedures	Dose 4		Dose 5		Dose 6		
Study Day	8	9	10	11	12	13	14
In Hours Post Dose 1	168	192	216	240	264	288	312
Concomitant Medications	X		X		X		
Adverse Events	X		X		X		
Physical Exam	C/S		S		S		
Height & Weight	W						
Vital Signs a & Oximetry	X		X		X		
Spirometry b	X						
Blood for Safety Labs c	X						
Urinalysis c	U						
Biomarkers c	X						
Study Drug Administration d	X		X		X		
Collect Samples for PK c	X		X		X		

Abbreviations: C = complete physical exam; PK = pharmacokinetic; S = symptom-directed physical exam; U = urinalysis (dipstick); W = weight  
NOTE: See also Protocol Section 7.4 for details on timing of assessments relative to study drug administration.  
a Includes blood pressure, heart rate, respiratory rate, and temperature.  
b Includes FEV1, FVC, and FEF25-75.  
c See Protocol Appendix 2 for a detailed schedule of these assessments, broken down by type of specimen and time relative to dose.  
d Subjects who are taking concurrent CF therapy should receive this therapy prior to study drug dosing in the order specified in Protocol Section 6.3.1.

**Table A.1-4: Multiple Ascending Dose Cohorts 5-8, WEEK 3**

Study Procedures	Dose 7		Dose 8		Dose 9		
Study Day	15	16	17	18	19	20	21
In Hours Post Dose 1	336	360	384	408	432	456	480
Concomitant Medications	X		X		X		
Adverse Events	X		X		X		
Physical Exam	C/S		S		S		
Height & Weight	W						
Vital Signs a & Oximetry	X		X		X		
Spirometry b	X						
CFQ-R RSS c	X						
Blood for Safety Labs d	X						
Urinalysis d	U						
Biomarkers d	X						
Study Drug Administration e	X		X		X		
Collect Samples for PK d	X		X		X		

Abbreviations: C = complete physical exam; CFQ-R RSS = Cystic Fibrosis Questionnaire-Revised Respiratory Symptom Score; PK = pharmacokinetic; S = symptom-directed physical exam; U = urinalysis (dipstick); W = weight  
NOTE: See also Protocol Section 7.4 for details on timing of assessments relative to study drug administration.  
a Includes blood pressure, heart rate, respiratory rate, and temperature.  
b Includes FEV1, FVC, and FEF25-75.  
c Should be completed prior to any other procedures or assessments.  
d See Appendix 2 for a detailed schedule of these assessments, broken down by type of specimen and time relative to dose.  
e Subjects who are taking concurrent CF therapy should receive this therapy prior to study drug dosing in the order specified in Protocol Section 6.3.1.

**Table A.1-5: Multiple Ascending Dose Cohorts 5-8, WEEK 4**

Study Procedures	Dose 10		Dose 11		Dose 12
Study Day	22	23	24	25	26
In Hours Post Dose 1	504	528	552	576	600
Concomitant Medications	X		X		X
Adverse Events	X		X		X
Physical Exam a	C/S		S		C/S
Height & Weight	W				W
Vital Signs b & Oximetry a	X		X		X
Spirometry a,c	X				X
Blood for Safety Labs d	X				
Urinalysis d	U				
Biomarkers d	X				
Sweat Chloride d					X
Study Drug Administration e	X		X		X
Collect Samples for PK d	X		X		X
Abbreviations: C = complete physical exam; PK = pharmacokinetic; S = symptom-directed physical exam; U = urinalysis (dipstick); W = weight a See Protocol Section 7.4 for details on timing of these assessments relative to study drug administration. b Includes blood pressure, heart rate, respiratory rate, and temperature. c Includes FEV1, FVC, and FEF25-75. d See Protocol Appendix 2 for a detailed schedule of these assessments, broken down by type of specimen and time relative to dose. e Subjects who are taking concurrent CF therapy should receive this therapy prior to study drug dosing in the order specified in Protocol Section 6.3.1					

**Table A.1-6: Multiple Ascending Dose Cohorts 5-8, Follow-Up Visits**

Study Procedures	PK Follow-up 24 Hours After Last Dose	PK Follow-up 96 Hours After Last Dose	7 Days After Last Dose (End of Treatment)	Follow-up 28 Days after Last Dose (End of Study)
Study Day	27 ± 1	30 ± 2	33	54
In Hours Post Dose 1	624 ± 12	696 ± 48	768	1272
Concomitant Medications			X	X
Adverse Events			X	X
Physical Exam			C	C
Height & Weight			W	W
Vital Signs a & Oximetry			X	X
Spirometry b			X	X
Chest Xray			X	
12-lead ECG			X	
CFQ-R RSS c			X	X
Blood for Safety Labs d			X	X
Urinalysis d			U	U
Pregnancy test d,e			X	X
Sputum for Microbiology d			X	
Biomarkers d			X	X
Sweat Chloride d			X	X
Collect Samples for PK d	X	X	X	X
Abbreviations: C = complete physical exam; CFQ-R RSS = Cystic Fibrosis Questionnaire-Revised Respiratory Symptom Score; PK = pharmacokinetic; U = urinalysis (dipstick); W = weight a Includes blood pressure, heart rate, respiratory rate, and temperature. b Includes FEV 1 , FVC, and FEF 25-75 . c Should be completed prior to any other procedures or assessments. d See Protocol Appendix 2 for a detailed schedule of these assessments, broken down by type of specimen and time relative to dose. e Pregnancy test (preferably serum but urine is accepted) required for women of child-bearing potential only.				

**APPENDIX 2: SCHEDULE OF LABORATORY TESTS**

**Table A.2-1: Single Ascending Dose Cohorts 1-4**

Labs	Screening	Check-In	Dose			Discharge				End of Study a
Study Day	≤-14 days b	-1	1	2	3	4	5	6	7	8
In Hours		-24	0	24	48	72	96	120	144	168
Hematology	X	X	X	X	X	X				X
Serum Chemistry	X	X	X	X	X	X				X
Hematology & Chemistry	Day 1: Pre-dose, 30, 60 minutes, 2, 4, 8, 12 hours post dose									
C-Reactive Protein		X	X	X						X
Erythrocyte Sedimentation Rate		X	X	X						X
C-Reactive Protein & Erythrocyte Sedimentation Rate	Day -1 Day 1: Pre-dose, 24 hours post dose									
Coagulation and CH50	X									X
Direct Antiglobulin Test	X									X
Serum Tocopherol (Vit. E)	X									
Urine microalbumin		X								X
Urinalysis	X	X	X	X	X	X				X
	Day 1: On pooled PK samples Day 2, 3, 4, 8: Random sample, preferably 1 st morning void									
Drug Screen	X c									
Pregnancy test d	X	X								X
Sputum for Microbiology		X								X
CFTR Genotyping e	X									
CFTR Sequencing		X f								
Sweat Chloride	X									
PK Sampling	Serum: 0, 0.5, 1, 2, 3, 4, 12, 24, 48, 54, 72, 168 hours post dose Urine: Pre-dose; Pooled from 0 to 4, 4 to 12, and 12 to 24 hours post-dose; and 48, 72, and 168 hours post dose (UA on each pooled sample). Sputum: 3 samples obtained within first 6 hours post dose; 24 hours post dose; Day 4 (72 hours post dose); and Day 8 (168 hours post dose)									
Serum for PK			X	X	X	X				X
Urine for PK			X	X	X	X				X
Sputum for PK			X g	X		X h				X g

Labs	Screening	Check-In	Dose			Discharge				End of Study a
Biomarker Sampling										
Blood (serum and plasma) for Biomarkers	X	X g		X		X				X
Sputum for Biomarkers	X	X g		X		X				X

a For subjects who withdraw prematurely from the study, this visit will occur whenever they leave the study.
 
b The screening period for an individual subject may be extended for an additional 7 days at the discretion of the Sponsor's Medical Monitor. See Protocol Section 7.2 for details.
 
c Drug screening may be performed on urine or blood sample.
 
d Women of child-bearing potential only
 
e Required if original documentation for CF genotyping is not available or is earlier than the year 2000.
 
f Samples may be collected on Day 1 pre-dose instead of Day -1.
 
g Suggest obtaining samples in conjunction with performing spirometry at 10, 60 minutes, and 4 hours post dose.
 
h Sample may be taken any time prior to discharge (Day 4) or during visit (End of Study).
										

**Table A.2-2: Multiple Ascending Dose Cohorts 5-8, WEEK 1**  
**Dosing Schedule assumes Monday-Wednesday-Friday dosing:**

Study Procedures	Screening		Dose 1	Dose 2		Dose 3		
Study Day	≤-14 days a	-1	1	3	4	5	6	7
In Hours		-24	0	48	72	96	120	144
Hematology	X	X	X	X	X			
Serum Chemistry	X	X	X	X	X			
Hematology & Chemistry	Dose 1: Pre-dose, 30, 60 minutes, 2, 4, 8, 12 hours post Dose 1 Dose 2: 60 minutes and 4 hours post Dose 2							
C-Reactive Protein		X	X					
Erythrocyte Sedimentation Rate		X	X					
C-Reactive Protein & Erythrocyte Sedimentation Rate	Day -1 Day 1: Pre-dose							
Coagulation and CH50	X							
Direct Antiglobulin Test	X							
Serum Tocopherol (Vit. E)	X							
Urine microalbumin		X						
Urinalysis	X	X	X	X	X			
	Dose 1: Pre-dose, 0-4, 4-12 hours post dose (UA on each pooled sample) Dose 2: 60 minutes and 4 hours post dose							
Drug Screen	X b							
Pregnancy Test c	X	X						
Sputum for Microbiology		X						
CFTR Genotyping d	X							
CFTR Sequencing		X e						
Sweat Chloride	X							
PK Sampling	Serum: 0, 0.5, 1, 2, 3, 4, 12; pre-Dose 2; 2 hours post Dose 2; 72 hours post Dose 1; 96 hours post Dose 1 (pre-Dose 3) Urine: Pre-dose; Pooled from 0 to 4 and 4 to 12 hours post Dose 1 (UA on each pooled sample). A separate sample should be collected at 24 and 72 hours post Dose 1. Sputum: 3 samples obtained within first 6 hours post Dose 1 and Day 4 (72 hours)							
Serum for PK			X	X	X	X		
Urine for PK			X		X			
Sputum for PK			X f		X			
Biomarker Sampling								
Blood (serum and plasma) for Biomarkers	X	X e			X			
Sputum for Biomarkers	X	X e			X			

a The screening period for an individual subject may be extended for an additional 7 days at the discretion of the Sponsor's Medical Monitor. See Protocol Section 7.2 for details.

b Drug screening may be performed on urine or blood sample.

c Women of child-bearing potential only.

d Required if original documentation for CF genotyping is not available or is earlier than the year 2000.

e Samples may be collected on Day 1 pre-dose instead of Day -1. Samples for CFTR sequencing should not be collected for subjects who participated in SAD cohort.

f Suggest obtaining samples in conjunction with performing spirometry at 10, 60 minutes, and 4 hours post dose.

**Table A.2-3: Multiple Ascending Dose Cohorts 5-8, WEEK 2**

Labs	Dose 4		Dose 5		Dose 6		
Study Day	8	9	10	11	12	13	14
In Hours	168	192	216	240	264	288	312
Hematology	X						
Serum Chemistry	X						
Hematology & Chemistry	Dose 4: Pre-dose, 15, 60 minutes, 2 hours post dose						
C-Reactive Protein	X						
Erythrocyte Sedimentation Rate	X						
C-Reactive Protein & Erythrocyte Sedimentation Rate	Dose 4: Pre-dose						
Coagulation and CH50	X						
Urine microalbumin			X				
Urinalysis	X						
	Dose 4: Pre-dose, 60 minutes and 2 hours post dose Dose 10: Urine microalbumin pre-dose						
PK Sampling	Serum: Prior to Dose 4, 5, and 6 Sputum: Prior to Doses 4, 5, and 6						
Serum for PK	X		X		X		
Sputum for PK	X		X		X		
Biomarker Sampling	Dose 4: Pre-dose						
Blood (serum and plasma) for Biomarkers	X						
Sputum for Biomarkers	X						

**Table A.2-4: Multiple Ascending Dose Cohorts 5-8, WEEK 3**

Study Procedures	Dose 7		Dose 8		Dose 9		
Study Day	15	16	17	18	19	20	21
In Hours	336	360	384	408	432	456	480
Hematology	X						
Serum Chemistry	X						
Hematology & Chemistry	Dose 7: Pre-dose, 15, 60 minutes, 2 hours post dose						
C-Reactive Protein	X						
Erythrocyte Sedimentation Rate	X						
C-Reactive Protein & Erythrocyte Sedimentation Rate	Dose 7: Pre-dose						
Urinalysis	X						
	Dose 7: Pre-dose, 60 minutes and 2 hours post dose						
PK Sampling	Serum: Prior to Dose 7, and 1 hours post Dose 7; Prior to Doses 8 and 9						
Serum for PK	X		X		X		
Biomarker Sampling	Dose 7: Predose						
Blood (serum and plasma) for Biomarkers	X						
Sputum for Biomarkers	X						

**Table A.2-5: Multiple Ascending Dose Cohorts 5-8, WEEK 4**

Study Procedures	Dose 10		Dose 11		Dose 12
Study Day	22	23	24	25	26
In Hours	504	528	552	576	600
Hematology	X				
Serum Chemistry	X				
Hematology & Chemistry	Dose 10: Pre-dose, 15, 60 minutes, 2 hours post dose				
C-Reactive Protein	X				
Erythrocyte Sedimentation Rate	X				
C-Reactive Protein & Erythrocyte Sedimentation Rate	Dose 10: Pre-dose				
Urinalysis	X				
	Dose 10: Pre-dose, 60 minutes and 2 hours post dose				
Sweat Chloride					X
PK Sampling	Serum: Pre-Dose 10 and 11; Dose 12 (pre-dose; post dose at 1, 2, 3, 4, 8 hours) Urine: Dose 12 pre-dose only				
Serum for PK	X		X		X
Urine for PK					X
Biomarker Sampling	Dose 10: Pre-dose				
Blood (serum and plasma) for Biomarkers	X				
Sputum for Biomarkers	X				

**Table A.2-6: Multiple Ascending Dose Cohorts 5-8, Follow-up**

Study Procedures	PK Follow-up 24 hours After Last Dose	PK Follow-up 96 Hours After Last Dose	7 Days After Last Dose (End of Treatment) a	28 Days After Last Dose (End of Study) a
Study Day	27	30	33	54
In Hours Post Dose 1	624 ± 12	696 ± 96	768	1272
Hematology			X	X
Serum Chemistry			X	X
C-Reactive Protein			X	
Erythrocyte Sedimentation Rate			X	
Coagulation and CH50			X	
Direct Antibody Test			X	
Urine microalbumin				X
Urinalysis			X	X
Pregnancy test b			X	X
Sputum for Microbiology			X	
Sweat Chloride			X	X
PK Sampling	Serum post last dose: 24 ±12 hrs, 96 ± 48, hours post last dose, and at End of Treatment and End of Study Visit Urine post last dose: 24 ±12 hrs, 96 ± 48, hours post last dose			
Serum for PK	X	X	X	X
Urine for PK	X	X		
Biomarker Sampling	End of Treatment and End of Study Visits			
Blood (serum and plasma) for Biomarkers			X	X
Sputum for Biomarkers			X	X

a See Protocol Section 5.5.2 for details on these visits for subjects who withdraw prematurely from the study.

b Women of child-bearing potential only

## 1. INTRODUCTION

The purpose of this statistical analysis plan (SAP) is to document post hoc analysis requested to be undertaken for the phase 1b, randomized, double-blind, Placebo-controlled, Dose-escalation study to evaluate the safety, tolerability and pharmacokinetics of QR-010 in subjects with homozygous  $\Delta F508$  cystic fibrosis, (PQ-010-001).

Reference is made to SAP V1.0, dated 18 April 2017.

## 2. SUBJECT POPULATIONS

### 2.1. Population Definitions (MAD)

Two new populations are introduced:

Per Protocol Population (MAD): The population for additional efficacy analyses consists of all subjects from the exploratory population that receive at least 10 out of 12 doses of QR-010 or placebo.

Subjects will be analyzed according to the actual treatment received.

Sensitivity Population for ppFEV1: This population consists of subjects from the Per Protocol Population, excluding outliers with a change from baseline in ppFEV1  $\geq 20$ .

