5.5.3.2 Stopping Rules for Individual Subjects

For individual subjects in the SAD cohorts, any of the criteria below will result in discontinuation of study drug administration in the SAD portion of the study, as well as exclusion from participation in the MAD portion. These subjects will continue to be followed for safety through the End of Study visit.

- Any SAE suspected of being related to study drug
- Any Grade ≥ 2 AE suspected of being related to study drug
- Decrease in absolute FEV₁ volume of $\geq 15\%$ from baseline value following study drug administration
- Unacceptable toxicity considered by the Investigator to be related to study drug treatment
- Further treatment is deemed to be unsafe in the Investigator's clinical judgment. The decision to discontinue a subject may also result from any clinically significant alteration in any clinical or laboratory finding
- If at any time the subject fails to follow the requirements of the protocol
- The subject withdraws consent. Subjects may withdraw from the study at any time without repercussion to their treatment or affiliation with their healthcare providers.

For individual subjects in the MAD cohorts, any of the following will result in permanent discontinuation of study drug:

- Any SAE suspected of being related to study drug
- Any Grade ≥ 2 AE suspected of being related to study drug
- Cumulative decrease in absolute FEV₁ volume of $\geq 15\%$ from baseline value following study drug administration
- Unacceptable toxicity considered by the Investigator to be related to study drug treatment
- Further treatment is deemed to be unsafe in the Investigator's clinical judgment. The decision to discontinue a subject may also result from any clinically significant alteration in any clinical or laboratory finding
- If at any time the subject fails to follow the requirements of the protocol
- The subject withdraws consent. Subjects may withdraw from the study at any time without repercussion to their treatment or affiliation with their healthcare providers.

If study drug is discontinued for any of these stopping rules, administration will not be resumed, even after resolution of the event.

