#### **4.2.2. Change (absolute) and % Change (relative change)**

Change and % change (relative) from baseline is calculated as:

Change = Post baseline visit value – baseline value.

% Change =  $100 * ((\text{Post baseline visit value} - \text{baseline value}) / \text{baseline value})$ .

If either the baseline or visit value is missing, the change from baseline/% change is set to “missing”.

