## 3. ANALYSES

### 3.1. ppFEV1 (%)

Descriptive summaries will be performed on Per Protocol Populations and Sensitivity Population excluding outliers of PPFEV1. Summaries will be repeated on subgroups of PPFEV1 at baseline for the 3 populations.

The mixed-model analysis described in the SAP will be repeated on the Per Protocol and Sensitivity Populations (using the following time points: Baseline, Day 4, Day 5 pre-dose, Day 8 pre-dose, Day 15 pre-dose, Day 22 pre-dose, Day 26 pre-dose, Day 26 4 hours post-dose, Day 33 and Day 54. Differences versus Placebo will be estimated at Day 15, Day 26 pre-dose, Day 26 4 hours post-dose, Day 33 and Day 54). Differences versus Placebo at Day 15 will also be assessed on Exploratory Population (in addition to planned time points).

The mixed model analysis will also be carried out on subgroups of PPFEV1 at baseline for the 3 populations. Due to the small sample size, the following time points only will be included in the model: Day 15 pre-dose, Day 26 pre-dose and Day 33.

The sensitivity analysis including presence/absence of *Pseudomonas aeruginosa* at Baseline as a covariate will be repeated on Per Protocol Populations. Day 15 will be added as time point of interest for both Exploratory and Per Protocol Populations.

Analyses to explore the dose response using the MCPMOD methodology as described in the SAP will be followed and repeated on Per Protocol Populations. The change from baseline in ppFEV1 at Day 15 pre-dose (also on Exploratory Population), Day 26 pre-dose, Day 26 4 hours post-dose, Day 33 and Day 54 will be assessed.

In addition to the dose-responses shapes described in the SAP, a quadratic model with umbrella-shape will be tested. Parameters of the dose-responses shapes models may be adapted to fit the data.

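### The post hoc Sensitivity Population drops subjects for large ppFEV1 gains, with no matching rule for falls and no named visit, and this can distort the mixed-model comparison with placebo

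*SAP*

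**What the plan says.** The addendum states that its purpose is "to document post hoc analysis requested to be undertaken". Its section 2.1 adds two MAD populations:

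- The Per Protocol Population is the subjects of the exploratory population "that receive at least 10 out of 12 doses of QR-010 or placebo".
- The Sensitivity Population for ppFEV1 is the Per Protocol subjects, "excluding outliers with a change from baseline in ppFEV1" of 20 or more.

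SAP 4.2.2 fixes the sign and scale: "Change = Post baseline visit value – baseline value", with percentage change defined separately. A change of 20 or more is therefore a gain of at least 20 percentage points. The addendum gives no lower limit, no visit at which the change is assessed and no reason for 20.

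Addendum 3.1 uses the set for descriptive summaries and for inference: "The mixed-model analysis described in the SAP will be repeated on the Per Protocol and Sensitivity Populations". Differences from placebo are estimated at Day 15, Day 26 pre-dose, Day 26 4 hours post-dose, Day 33 and Day 54. The model is also refitted within baseline ppFEV1 subgroups for all three populations.

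Protocol 5.5.3.2 stops study drug permanently in a MAD subject whose FEV1 volume has fallen by 15% or more from baseline, and adds: "If study drug is discontinued for any of these stopping rules, administration will not be resumed".

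**The concern.** A subject leaves this set because of the value of the variable that the model is fitted to, measured after treatment, and only if that value is high. Such a cut lowers each arm's mean by an amount that depends on how much of the arm lies near +20. The arms are affected equally only if their distributions are the same. If they are not, the estimated difference moves, and the standard errors come from a spread that has been artificially reduced.

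The arms are small, so one or two exclusions could decide what the sensitivity analysis appears to show. The rule is post hoc, and Protocol 4.2 has the sponsor unblinded during the study. A one-tailed cut in that setting is hard to defend even if it was made in good faith. Because no visit is named, two analysts could also build different sets from the same data.

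**Working it through.** The plan states no SD, power or expected exclusion count for this set, so it has no figure to reproduce.

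**Inputs.** The cut is at +20 points (addendum 2.1, SAP 4.2.2). Planned MAD arms are 6 per dose and 4 x 2 = 8 pooled placebo (SAP 4.1, Table 4). The SD of the ppFEV1 change is an assumption, taken over 5 to 12 points.

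**Step 1: effect of the cut at one time point.** For a normal change with mean m and SD s, the mean after removing values of 20 or more is m - s x phi(a)/Phi(a), with a = (20 - m)/s.

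Example with s = 10 and a true difference of 7:
- Active: a = 1.3, so 7 - 10 x 0.1714/0.9032 = 5.103; 9.7% are excluded.
- Placebo: a = 2, so 0 - 10 x 0.0540/0.9772 = -0.552; 2.3% are excluded.
- Difference: 5.103 + 0.552 = 5.66 instead of 7.

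The last column shows a cut at 20 or more in either direction.

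| SD active / placebo | True difference | Gains of 20+ removed | Changes of 20+ either way removed |
|---|---|---|---|
| equal, any tried | 0 | 0.00 | 0.00 |
| 5 / 5 | 5 | 4.98 | 4.98 |
| 8 / 8 | 5 | 4.57 | 4.46 |
| 10 / 10 | 5 | 4.16 | 3.79 |
| 12 / 12 | 5 | 3.80 | 3.12 |
| 10 / 10 | 7 | 5.66 | 5.21 |
| 12 / 8 | 0 | -1.11 | 0.00 |
| 8 / 12 | 0 | +1.11 | 0.00 |

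**Step 2: one subject.** Removing a subject with change x from an arm of n, when the others average m, lowers the arm mean by (x - m)/n. With x = 20 and m = 0:
- One of 6 on active: 20/6 = 3.3, so the contrast falls by 3.3 points.
- One of 8 on placebo: 20/8 = 2.5, so every active-placebo contrast rises by 2.5 points.

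These are raw means. The baseline-adjusted mixed model would give somewhat different shifts.

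**Step 3: which large falls remain.** With an unchanged predicted value, a 20-point fall is a relative fall of 20/baseline: 28.6% from 70, 20% from 100 and 15% from 133. It therefore meets the 15% stopping rule at any baseline up to about 133. Day 22 is dose 10. A fall seen by Day 22 pre-dose leaves at most 9 doses and the subject is not Per Protocol. A fall first seen after dose 10 leaves at least 10 doses if none was missed, and the subject stays in. Of the five placebo contrasts, only Day 15 precedes dose 10.

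**Step 4: simulation over the nine post-baseline time points of the addendum's model.** Assumptions: SD 8, correlation 0.6, baseline uniform from 70 to 115, exclusion if any visit reaches +20, difference read at Day 26 pre-dose.
- With no effect, the share of kept placebo subjects with a late fall of 20 or more is 2.1% without the stopping rule and 0.5% with it.
- With a true effect of 5 and no stopping rule, the estimate goes from 4.98 (Per Protocol) to 3.95. The loss is 1.03 points, against 0.43 in Step 1, so the unnamed visit matters.
- With the stopping rule applied, it goes from 4.15 to 3.13, a loss of 1.02.

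**The case against.** The strongest case on the other side has five parts.

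- **The falls are dealt with elsewhere.** The stopping rule and the 10-dose requirement already act on the lower tail. This stands for falls seen up to Day 22 pre-dose, so it would be wrong to infer that the set keeps all falls as large as the gains it drops. It does not cover falls first seen later.
- **The bias is conditional.** A reader might infer that the placebo comparison is necessarily biased. It is not: when both arms have the same distribution the difference is unchanged. The direction is not fixed either. With the stopping rule applied, no effect and active SD 1.3 times the placebo SD of 8, the simulated Per Protocol difference is already +1.57, and the upper cut brings it to +0.12. That is an accidental offset of one selection by another, which cannot be relied on.
- **Symmetry is not the cure.** A reader might infer that the missing mirror rule is the whole fault. The table shows that a two-sided cut removes the false difference due to unequal spread, but shrinks a real effect slightly more.
- **No effect-size threshold is applied here.** The shifts in Step 2 are close to 3 points, the smallest size of interest in SAP 4.8.1.1. That threshold belongs to the MCPMod analyses, and addendum 3.1 does not name the Sensitivity Population for those.
- **Little depends on it.** The analysis is post hoc, on an exploratory endpoint, and is shown beside Exploratory and Per Protocol results that keep these subjects. MTD and dose escalation do not use it. All of this stands and limits the importance of the point.

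The rule may have been meant in absolute value, but the addendum does not say so. Where the SAP means a fall it writes the minus sign (4.10.1.4). Nor do the documents show that the cut was chosen to remove known subjects; they show only that unblinded knowledge was possible.

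**Conclusion.** The point holds as a conditional one. The Sensitivity Population is selected on the upper tail of the outcome, with no visit named, and is then used to estimate differences from placebo. That can give a wrong comparison. Under the assumed SDs, a true difference of 5 points loses 0.02 to 1.20 points at a single time point (SD 5 to 12), and about 1 point at SD 8 if any visit counts. With no true effect, SDs of 8 and 12 give a false difference of about 1.1 points, in a direction set by which arm is wider. At planned arm sizes a single exclusion can move a contrast by 2.5 to 3.3 points.

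The SDs, correlation and normal shape are assumptions. The arm sizes are the planned ones, and actual Per Protocol arms may differ. The stopping-rule argument assumes that the rule was followed. The consequence is confined to the reading of one post hoc exploratory analysis, but that analysis is meant to show robustness, and the rule makes it unsuited to that purpose.

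**What to change.** Replace the exclusion with an analysis that keeps all Per Protocol subjects:

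1. Fit a robust or rank-based version of the ppFEV1 mixed model.
2. Refit the planned model leaving out one subject at a time, and report the range of each placebo contrast and the arm of the most influential subjects.

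If an exclusion set is still shown, define it on the absolute size of the change, in percentage points, at one named visit. Give the reason for 20, report exclusions by arm, and place the Exploratory and Per Protocol estimates beside it. State that a symmetric cut removes the artefact of unequal spread but still attenuates a real effect.

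The cost is one change of definition and one rerun on a MAD part planned at 32 subjects. No new data are needed.
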